1.5. Endpoints

The primary efficacy endpoint is the sensitivity and accuracy of detection of patients with myocardial dysfunction using MyoStrain® compared to standard assessments of cardiac function: left ventricular ejection fraction (LVEF), as well as end-systolic (LVESV), end-diastolic (LVEDV), and stroke (LVSV) volumes indexed to body surface area.

Changes in function based on clinical presentation, standard assessments, and all available metrics will be used to define the cardiotoxicity status of the patient. A clinical committee organized and chaired by the principal investigator will be used to classify each exam in both unblinded and blinded arms according to professional knowledge and derived from the ASE Expert Consensus Position Paper, the ESC Position Paper, and the ESMO Clinical Practice Guidelines. [1] [2] [3]

- Clinical cardiac dysfunction is defined as an absolute change in LVEF > 10% from baseline to below 53% combined with heart failure symptoms or abnormal cardiac biomarkers (troponin, BNP, or NT pro BNP).
- Subclinical CTX was defined as an asymptomatic patient with a greater than 15% decrease in LVEF that remains >= 53%, worsening GLS more than 15% from baseline, or abnormal cardiac biomarkers (troponin, BNP, or NT pro BNP).
- If no baseline information is available to compare metrics for categorizing cardiotoxicity status, considering most patients in the PROACT sub-study of the Survive Registry will have metastatic cancer with prior treatments including chemotherapy, physician discretion and patient presentation will provide the final decision on cardiotoxicity category. All available metrics will be used to classify patients at each assessment time point.

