2.3. PROACT Pilot Clinical Testing

A single center, pilot study was performed to evaluate the ability of the MyoStrain® MRI software system to identify cardiotoxicity during cardio-oncology treatment of breast cancer and lymphoma patients. An interim analysis of 15 subjects from the PROACT Pilot study (VAL-1005P) is included below to provide additional clinical evidence that the MyoStrain® software is able to detect progression of myocardial dysfunction resulting from cardiotoxicity. The pilot study was performed by Principal Investigator Hr. Priv.-Doz. [name] (Facharzt für Innere Medizin, Kardiologie PD DR) at Marien Krankenhaus GmbH (Hamburg, Germany).

- **Patient Demographics**

Demographic	Average ± St Dev
Age (years)	52.2 ± 11.5
Body Surface Area (m ²)	1.8 ± 0.2
Body Mass Index (kg/m ²)	25.7 ± 4.7
History of Cancer (months)	1.4 ± 0.8
Charlson Comorbidity Index	1.4 ± 1.0

- **Baseline CMR Information**

Baseline CMR Information	Average ± St Dev
LVEF (%)	58.8 ± 5.3
LVEDV Index (ml/m ²)	77.6 ± 13.4
LVESV Index (ml/m ²)	32.1 ± 8.0
Stroke Volume Index (ml/m ²)	45.5 ± 7.8
T1 Value Pre-Contrast (msec)	1052.4 ± 44.6
T1 St Dev Pre-Contrast (msec)	52.4 ± 11.8
Global Longitudinal Strain (%)	-20.8 ± 1.9
Global Circumferential Strain (%)	-19.0 ± 1.8

# Segments > -10%	1.7 ± 1.5
# Segments > -17%	8.5 ± 4.7

- Baseline Risk Assessment of Developing Cardiotoxicity by Segmental MyoStrain®.** Patients were stratified as to their risk by the number of dysfunctional (> -10%) and abnormal segments (> -17%). These thresholds have been validated as previously described in Figure 1 above.

[figure not shown]
Cardiotoxicity Risk Level	Segmental MyoStrain® Criteria	Incidence
Low	≤ 1 Segment > -10% & < 9 Segments > -17%	46% (7/15)
Moderate	2-3 Segments > -10% or 9+ Segments > -17%	27% (4/15)
High	3+ Segments > -10% & 10+ Segments > -17%	27% (4/15)

- Baseline Echocardiography Data**

[figure not shown]
Baseline Echocardiography Data	Average \pm St Dev
LVEF (%)	63.9 ± 5.8
LVEDV Index (ml/m ²)	47.7 ± 10.1
LVESV Index (ml/m ²)	17.3 ± 6.4
Stroke Volume Index (ml/m ²)	30.3 ± 5.1
GLS (%)	-26.5 ± 14.6
E/E'	8.8 ± 2.0

Pts with Poor Acoustic Window: 4/14 (29%)

- Interim Results of Segmental Dysfunction and Global Measures Throughout Follow-up**

[figure not shown]

- Interim Results of Global Strain Evolution Throughout Follow-up

- Example of Low Risk Patient Not Experiencing Cardiotoxicity.

[figure not shown]

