5. STUDY DESIGN

5.1. Summary Protocol

Patients with any type of cancer scheduled to receive anti-cancer therapy with or without concomitant radiotherapy and enrolled in the SURVIVE Registry will be evaluated based on baseline MyoStrain® segmental dysfunction risk profile. After consenting to the PROACT study, patients will undergo a baseline MRI to determine their risk stratification for the study. This baseline MyoStrain® MRI must demonstrate 2 or more segments measuring >-10% or 9 or more segments >-17% for entrance into the study.

[figure not shown]
Eligible patients will then be randomized 1:1 into the MyoStrain® guided treatment arm versus the Myostrain® blinded observational arm, as shown in Figure 2. The treatment arm will guide patient management by augmenting standard of care with serial MyoStrain® monitoring of the impact of cancer therapy on myocardial function by providing physicians with MyoStrain® values, in addition to LVEF, LVEDV, and LVESV. In the

observational arm, physicians will only be provided with LVEF, LVEDV, and LVESV, which are clinical measurements. The standard of care assessments by cardiac MRI, will not include MyoStrain® assessments.

In order to obtain the MyoStrain® values, MRI images obtained will be uploaded de-identified to Myocardial Solutions, Inc. After the baseline scan, Myocardial Solutions, Inc. will inform research staff whether the patient met criteria for continued follow up in the study. At that time, the patient will be randomized to one of the two arms, as previously described, and Myocardial Solutions, Inc. will be made aware of the randomization result. If randomized to the blinded observational arm, no results from any cardiac MRI obtained for the study will be provided to physicians from Myocardial Solutions, Inc. If randomized to the MyoStrain® guided treatment arm, MyoStrain® results and LVEF, LVEDV, and LVESV will be provided for all cardiac MRI's obtained in the study to the physicians. Sites will also send Myocardial Solutions, Inc. de-identified information about the patients' medical history (i.e. comorbidities, past/current medications, etc.).

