During the SENC MyoStrain® Test analysis, each mesh applied to the dataset will populate the appropriate model in the Measures section. The color legend in Figure 3 provides a basic guide to the meaning of each color. The coloring shown demarcates specific regions validated in published literature based on levels of myocardial function. Normokinetic defines strain < -17% while Akinetic defines strain > -10%. The numeric strain values for each segment and global measurements will also be displayed on the report. Alternative coloring schemes may be utilized depending on operator preference.

Figure 3: Color Legend for Strain Test

The Measures section SENC MyoStrain® exams will display resting strain, as well as global circumferential and longitudinal strain as shown in Figure 4.

Global MyoStrain Measures

Strain Measures			Traditional Measures		
	Raw	Normal		Raw	Index
Global Longitudinal Strain (GLS)	-21.8 %	(<-17)	LVEF	67.6 %	- (53-74)
Global Circumferential Strain (GCS)	-20.4 %	(<-17)	LVED Mass	87.2 g	- (39-75)
			LVES Mass	110.3 g	- (39-75)
			LVED Volume	156 ml	- (53-99)
			LVES Volume	50.5 ml	- (15-40)
			LV Stroke Volume	105.4 ml	- (35-63)

[figure not shown]
Resting MyoStrain Measures

Figure 4: Example Strain exam with 6 views quantified

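### The reference status for the Section 1.5 accuracy endpoint contains LVEF, a comparator, and may contain MyoStrain output; no committee masking is stated, so incorporation bias of undetermined size and direction is possible

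*Combined protocol and SAP*

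**What the plan says.** Section 1.5 sets the primary efficacy endpoint as sensitivity and accuracy of detecting myocardial dysfunction "using MyoStrain® compared to standard assessments of cardiac function: left ventricular ejection fraction (LVEF"), together with indexed end-systolic, end-diastolic and stroke volumes.

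The same section then defines the status against which detection is judged: "Changes in function based on clinical presentation, standard assessments, and all available metrics will be used to define the cardiotoxicity status of the patient". Two categories have written rules:

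- Clinical cardiac dysfunction: "an absolute change in LVEF > 10% from baseline to below 53% combined with heart failure symptoms or abnormal cardiac biomarkers".
- Subclinical cardiotoxicity, in an asymptomatic patient: an LVEF decrease of more than 15% that stays at or above 53%, or "worsening GLS more than 15% from baseline, or abnormal cardiac biomarkers".

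On who decides: "A clinical committee organized and chaired by the principal investigator will be used to classify each exam in both unblinded and blinded arms". The committee also draws on professional knowledge and cited guidelines. Where there is no baseline to compare with, the final call rests on physician discretion and presentation. Section 11 repeats the committee role with four categories at each exam.

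On strain: "The Measures section SENC MyoStrain® exams will display resting strain, as well as global circumferential and longitudinal strain" (Section 5.2).

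On blinding: for the observational arm, "no results from any cardiac MRI obtained for the study will be provided to physicians from Myocardial Solutions, Inc" (Section 5.1). Section 11 adds that those patients and their doctors see only four cardiac measures, and that the study team gets the remaining data at the end of the trial.

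**The concern.** A diagnostic accuracy comparison needs a reference that does not depend on the tests being compared. If one test helps to decide who counts as positive, it will agree with that decision partly because it was used to make it, and its sensitivity and specificity are distorted. Here one side of the comparison (LVEF) is certainly in the reference. The other side (MyoStrain) may be, through GLS or through the open-ended permission to use every metric to hand.

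Objective 2, detection of subclinical dysfunction compared with standard imaging, depends on this comparison. So do the ROC and precision-recall comparisons of strain changes with standard assessments in Section 11. If the reference is not kept separate, a reported difference between MyoStrain and LVEF could reflect how the categories were built rather than how well either test detects dysfunction.

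**Working it through.** **The plan's own figure.** The only design calculation is in Section 11, for the number of dysfunctional segments at 6 months: means 16.8 and 12.8 (difference 4.0), SD (4.7 + 7.8)/2 = 6.25, 5% level, 90% power. Taking the test as two-sided, total N = 4 × [6.25 × (1.960 + 1.282)/4.0]² = 102.6, which agrees with the stated 102. That endpoint does not use the committee's classification, so it neither supports nor weakens this point. No calculation is given for the Section 1.5 endpoint.

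**The overlap, element by element.**

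| Element | Role in the comparison | Role in the reference |
|---|---|---|
| LVEF | Comparator (1.5) | In the written clinical definition; one of three subclinical routes (1.5) |
| LV volumes | Comparators (1.5) | In no written rule, but covered by the general wording of 1.5 |
| GLS | MyoStrain output (5.2); strain changes are analysed as tests (11) | Enough alone for subclinical status (1.5); source not stated |
| MyoStrain segment data | Index test with cutoffs (11) | Not listed, but nothing excludes it |
| Symptoms, biomarkers | Neither test | In the written rules (1.5) |

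**GLS source.** Section 2.3 shows that the pilot recorded GLS by both cardiac MRI (-20.8 ± 1.9) and echocardiography (-26.5 ± 14.6), so either is possible. MyoStrain MRI is the only imaging on the PROACT schedule in Section 5.1. That makes MyoStrain GLS plausible without settling the question.

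**LVEF in the clinical category.** No positivity rule is given for LVEF as a comparator. If it is called positive by the same rule as in the definition, and the committee follows that definition, every clinical-category exam is LVEF-positive. Its sensitivity there is then 100% by construction.

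**Masking and timing.** The stated blinding covers observational-arm patients and physicians. The committee is not mentioned. Observational-arm MyoStrain data are released at the end of the trial, while guided-arm results go to physicians throughout. The documents do not say when exams are classified. If this happens before the release, MyoStrain could inform the reference in one arm only.

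**Can a direction be derived?** The documents give no prevalence, sensitivity or specificity, so all inputs in this illustration are assumed. Take MyoStrain, LVEF and a biomarker as equally good (sensitivity 0.60, specificity 0.90), conditionally independent, with prevalence 0.20. The true MyoStrain-minus-LVEF difference is 0.

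Reference = biomarker or LVEF:

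- P(reference positive) = 0.20 × (1 − 0.40²) + 0.80 × (1 − 0.90²) = 0.168 + 0.152 = 0.320.
- LVEF sensitivity = (0.20 × 0.60 + 0.80 × 0.10)/0.320 = 0.200/0.320 = 0.625.
- MyoStrain sensitivity = (0.20 × 0.60 × 0.84 + 0.80 × 0.10 × 0.19)/0.320 = 0.116/0.320 = 0.363.
- Apparent difference = −0.26.

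With biomarker or MyoStrain as the reference, the roles swap and the difference is +0.26. With all three in the reference, the difference is 0, but each test's specificity becomes 1.00 by construction. This shows only that the sign depends on which components the committee uses, which the plan leaves open. It does not estimate the bias in this trial.

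**The case against.** Guideline-based adjudication using LVEF, strain, symptoms and biomarkers is a reasonable clinical choice, and no perfect reference exists. The committee is not bound by the bullets: professional knowledge and the no-baseline discretion route can loosen the link with LVEF. GLS may be echocardiographic, and if the committee also sees no MyoStrain output, the direct MyoStrain overlap vanishes. The Section 11 cutoffs use the percentage of segments at or below -17%, not GLS change, so even MyoStrain GLS would overlap with them only in part. All of this stands. It limits the point but does not remove it, because the plan settles neither the GLS source nor what the committee sees, and LVEF is in the written rules in any case.

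Three stronger readings are tempting, and the documents do not support them.

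- A reader might infer that the bias favours MyoStrain in the subclinical category. That depends on how well MyoStrain detects patients who are positive by other routes. As an illustration, assume GLS worsening in 15% of exams, independent other positives in 20%, a correlation of 0.5 between the segment test and GLS change, and a MyoStrain sensitivity of 0.80 for the other positives. Adding GLS to the reference then changes apparent sensitivity by −7, −2 or +2 points at overall MyoStrain positivity of 0.30, 0.42 or 0.58. The sign is not fixed.
- A reader might infer that LVEF sensitivity for clinical dysfunction is simply 100%. That holds only under the two conditions given in the working, the same rule and strict adherence to it.
- A reader might infer that the committee is unmasked or that the reference does differ by arm. The text is silent on masking and timing; it does not say that either occurs.

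**Conclusion.** The point holds as an unprotected design feature of the Section 1.5 endpoint. That LVEF is both comparator and reference component is plain from the text and needs no assumption. That MyoStrain enters the reference is possible but not established: it requires MyoStrain GLS to be counted, or the committee to see MyoStrain output. A difference in the reference by arm additionally requires classification before the observational-arm data are released.

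No numerical size or net direction can be defended from the documents. The scope is also limited. Section 11 names a different primary endpoint, the 6-month segment count, and that randomised comparison is unaffected. This should be fixed, but it does not undermine the whole trial.

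**What to change.** In Section 1.5 and Section 11:

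1. Have the committee classify every exam in both arms, at the same stage, from a packet without MyoStrain strain output (GLS, global circumferential strain, segment data) and without arm. Count GLS only when it comes from a recorded non-MyoStrain source.
2. Use that classification for the MyoStrain accuracy analysis. Keep the classification from all metrics as a sensitivity analysis.
3. Pre-specify when LVEF and each volume count as positive. State that the MyoStrain-versus-LVEF difference will not be read as a fair head-to-head in categories whose definition contains LVEF.

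A comparison against symptoms and biomarkers alone would contain neither test, but it should be optional and exploratory. Biomarkers are not on the PROACT schedule, although they may come from the registry, whose protocol is not supplied.

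The cost is redaction work, a record of each GLS source, and endpoint wording; no visits or scans are added. The downside is possibly fewer reference-positive exams and wider intervals. Echocardiographic GLS might recover some of these, but the pilot reports poor acoustic windows in 4 of 14 patients (29%).

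Separately, the category definitions in Section 1.5 and the four categories in Section 11 need to be reconciled, because the written rules can overlap and can leave exams unclassified. That is a different issue and adds no weight here.

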Patient's will continue to undergo MyoStrain® MRI testing, regardless of study arm, at 1 month (\pm 2 weeks), 3 months (\pm 2 weeks), 6 months (\pm 2 weeks), 12 months (\pm 30 days), 24 months (\pm 30 days), and 36 months (\pm 30 days) after the baseline visit. In addition to the MyoStrain® testing, patients will also be asked to complete a brief patient satisfaction questionnaire at each PROACT time point. Patient's will already be completing the EQ-5D Questionnaire and the Cardiovascular Risk Assessment Questionnaire as part of the SURVIVE Registry protocol at the baseline, 6 month, 12 month, 24 month, and 36 month time points.

In addition to Myocardial Solutions, Inc. reviewing the cardiac MRI images, due to the multi-departmental nature of this study, sites may also choose to obtain a clinical read on the research cardiac MR images obtained on the short axis, which are the same images that would be obtained in a clinical MRI, and provide only the LVEF, LVEDV, and LVESV for all subjects, regardless of randomization arm, and those values may be uploaded to the patients' medical record, if permitted. Doing so would then allow patients' oncology team access to this information in lieu of obtaining additional testing (i.e. clinical cardiac MRI's, echocardiograms, etc.) to obtain this same information.

EXAMPLE OF GENERAL PRINCIPLES FOR CLINICAL DECISIONS WITH MYOSTRAIN® RESULTS:

- Worsening segment abnormalities, consider cardio-protective therapies.
- Advise oncology about developing toxicities.
- Enhance patient education (symptom awareness).

Figure 2 – Study Flow Diagram

PROACT Schedule of Events		Baseline	1 Month (±2 weeks)	3 Month (±2 weeks)	6 Month (±2 weeks)	12 month (±30 days)	24 month (±30 days)	36 month (±30 days)
PROACT Informed Consent		✓						
Inclusion/Exclusion Criteria Confirmation		✓						
MyoStrain® MRI Testing		✓	✓	✓	✓	✓	✓	✓
Randomization		✓						
Patient Satisfaction Questionnaire		✓	✓	✓	✓	✓	✓	✓

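### An abnormal biomarker alone makes an asymptomatic patient subclinical CTX, with no change-from-baseline condition, so a stable pre-existing abnormality is labelled toxicity

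*Combined protocol and SAP*

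**What the plan says.** Section 1.5 (Endpoints) defines the categories that a clinical committee, chaired by the principal investigator, assigns at each exam in both arms.

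- Subclinical category: "Subclinical CTX was defined as an asymptomatic patient with a greater than 15% decrease in LVEF that remains >= 53"%, or "worsening GLS more than 15% from baseline, or abnormal cardiac biomarkers (troponin, BNP, or NT pro BNP"). The three criteria are alternatives.
- Clinical category: "absolute change in LVEF > 10% from baseline to below 53% combined with heart failure symptoms or abnormal cardiac biomarkers".
- Evidence used: "All available metrics will be used to classify patients at each assessment time point".
- Population: "most patients in the PROACT sub-study of the Survive Registry will have metastatic cancer with prior treatments including chemotherapy".

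Section 11 repeats that cardiotoxicity status at each exam is the committee's category. Biomarkers are named only in 1.5. They do not appear in the eligibility criteria (1.6, 1.7, 5.4, 5.5), the Schedule of Events in 5.1, or the statistical section. The only registry data collection that 5.1 describes is two questionnaires.

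**The concern.** The committee category is the reference against which MyoStrain and the standard measures are judged, and detecting subclinical dysfunction is the second primary objective. A reference meant to capture the cardiac effect of therapy should not turn positive on a finding that was there before that therapy and has not moved. The biomarker criterion allows this. It sets no cutoff, no comparison with an earlier value, and no rule for a value already abnormal at entry.

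There is a second, more conditional issue. If no sampling is scheduled, a biomarker result exists only when someone orders it. The trial is open label and only guided-arm physicians see MyoStrain values, so ordering could differ between arms. The chance of being labelled positive could then differ as well.

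**Working it through.** **Inputs from the documents.** 40 evaluable patients randomized 1:1 (5.7), so 20 per arm. Seven exams: baseline and 1, 3, 6, 12, 24 and 36 months (5.1). 40 × 7 = 280 exams. The plan gives no figure on this point to reproduce. Its one power calculation (section 11) concerns the count of dysfunctional segments at 6 months and uses no biomarkers.

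**Step 1: the criteria side by side (1.5).**

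- LVEF, subclinical: requires a decrease.
- GLS, subclinical: requires worsening, expressly from baseline.
- Biomarker, clinical category: counts only together with an LVEF change from baseline.
- Biomarker, subclinical category: abnormal is enough. No change is required and no other finding is needed.

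**Step 2: trace one patient.** Take an asymptomatic, pretreated patient whose NT-proBNP is abnormal before the scheduled therapy and stays the same, with unchanged LVEF and GLS. The LVEF and GLS criteria are not met and the biomarker criterion is. As written, the patient is subclinical CTX at baseline and at each later exam with a measurement. Nothing in eligibility keeps this patient out.

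**Step 3: how many labels.** Assume a share q of patients is like this, with q = 10% to 30% (not in the documents).

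- Patients: 40 × 0.10 = 4 to 40 × 0.30 = 12.
- Exams, if a value exists at all seven: 4 × 7 = 28 to 12 × 7 = 84 of 280. This is an upper bound, because it also assumes no death, dropout or skipped MRI.
- If only 40% of exams have a value (assumption): 28 × 0.4 ≈ 11 to 84 × 0.4 ≈ 34.

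**Step 4: what unequal testing could do.** If a share t is tested, the share labelled without new toxicity is q × t. Take t = 80% in the guided arm and 40% in the observational arm (assumption):

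- q = 10%: 8% against 4% (1.6 against 0.8 of 20 patients)
- q = 20%: 16% against 8% (3.2 against 1.6)
- q = 30%: 24% against 12% (4.8 against 2.4)

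The spurious arm difference is 4, 8 or 12 percentage points. With equal testing it is zero, but the wrong labels remain in both arms.

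**Step 5: direction of the effect on apparent MyoStrain sensitivity.** Assume true subclinical CTX p = 20%, MyoStrain sensitivity Se = 85% and specificity Sp = 80%, and that every true case is reference-positive.

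(a) Testing unrelated to the MyoStrain result. With m = q × t,

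apparent sensitivity = [p·Se + (1−p)·m·(1−Sp)] / [p + (1−p)·m].

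- q = 10%: 0.760 at t = 40%, 0.664 at t = 100%
- q = 20%: 0.692 and 0.561
- q = 30%: 0.639 and 0.495

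Check for q = 30%, t = 100%: (0.17 + 0.048) / (0.20 + 0.24) = 0.495. Sensitivity falls from 0.85.

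(b) Opposite extreme: tests ordered only when MyoStrain is abnormal. Every wrong label is then MyoStrain-positive, and apparent sensitivity = [p·Se + (1−p)·q·(1−Sp)] / [p + (1−p)·q·(1−Sp)].

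- q = 10%: (0.17 + 0.016) / (0.20 + 0.016) = 0.861
- q = 30%: (0.17 + 0.048) / (0.20 + 0.048) = 0.879

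Sensitivity rises. The sign therefore depends on how tests are ordered, which the documents do not state.

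**The case against.** The strongest defence is that a committee, not an algorithm, assigns the category. Section 1.5 opens with "Changes in function based on clinical presentation, standard assessments, and all available metrics will be used to define the cardiotoxicity status of the patient", cites three external guidance papers, and relies on professional knowledge. Section 11 also offers a category for decline in function that is not attributed to cardiotoxicity. A sensible committee could discount a long-standing raised NT-proBNP. That is true, but nothing requires it to, and the specific definition says otherwise. A general framing sentence does not supply the missing condition.

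Several limits do stand:

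- A reader might infer that biomarkers are never sampled on schedule. The documents show this only for PROACT. The SURVIVE Registry protocol is not supplied and may provide sampling. If it does, a cross-reference settles that half, but the change rule is still missing.
- A reader might infer that guided-arm testing will be heavier and will inflate MyoStrain sensitivity. The items in 5.1, such as "Worsening segment abnormalities, consider cardio-protective therapies" and "Enhance patient education (symptom awareness"), are offered as examples of general principles, and neither mentions ordering biomarkers. Arm-dependent testing is a possibility, not a finding, and step 5 shows that the net direction is open.
- A reader might infer that prompting symptom reports creates reference-positive exams. The subclinical category requires an asymptomatic patient, so a symptom report takes the patient out of it. Symptoms create a clinical positive only if LVEF has also fallen by more than 10% to below 53%.
- The 6-month segment count powered in section 11 is unaffected. The accuracy endpoint in 1.5 also speaks of myocardial dysfunction generally. A raised biomarker before therapy may reflect real dysfunction, but it is not evidence of toxicity from the therapy under study.

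**Conclusion.** The point holds on the text. Followed as written, section 1.5 labels a stable, pre-existing biomarker abnormality as subclinical CTX, including at baseline. This is a stated rule that gives a wrong label, not just missing detail, and it should be corrected before exams are classified.

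The number affected is unknown. Under an assumed prevalence of 10% to 30% it is 4 to 12 of 40 patients. The figure of 28 to 84 of 280 exams is a ceiling that needs a biomarker value at every visit, and should not be read as an estimate. Differential testing between arms depends on sampling being unscheduled and on physician behaviour that the documents do not describe. Neither its size nor its net effect on MyoStrain sensitivity can be determined from them.

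**What to change.** In section 1.5:

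1. Change the biomarker criterion to newly abnormal, or increased from the pre-therapy value by a margin fixed before any exam is classified.
2. Class an abnormality present at the PROACT baseline as pre-existing, not CTX.
3. Where there is no pre-therapy value, or no test at that exam, treat the biomarker component as not evaluable: neither positive nor negative.

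In section 11: report the number of exams with a biomarker value by arm, and add a sensitivity analysis that leaves out exams positive on the biomarker alone. If the registry schedules sampling, cite it in 5.1.

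Do not answer the problem by making an MRI-only reference the main analysis. GLS is a MyoStrain output (2.1, 5.2) and LVEF is a comparator (1.5), so the reference would then consist only of the test under evaluation and what it is compared with.

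Cost: endpoint wording, one table and one extra analysis, with no added blood draws. Fewer exams will be reference-positive, so the interval around sensitivity widens, and some exams will not be evaluable on the biomarker component.

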2. DEVICE DESCRIPTION

For all patients undergoing a cardiac MRI, a standard non-contrast protocol will be used to acquire a full cardiac volume for chamber sizes and LVEF in the short axis as the initial scan.

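### The reference for the primary sensitivity and accuracy endpoint falls back on physician discretion when baseline is missing, yet baseline is undefined and every randomised patient has a PROACT baseline MRI

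*Combined protocol and SAP*

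**What the plan says.** Section 1.5 (Endpoints) compares MyoStrain with LVEF and ventricular volumes on sensitivity and accuracy for myocardial dysfunction. The reference is a cardiotoxicity category given to each exam in both arms by a committee that the principal investigator chairs. The imaging criteria are falls in LVEF and worsening of GLS, to be combined with symptoms or biomarkers or read alongside them. All available metrics may be used.

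The same section adds an exception. Its trigger is "If no baseline information is available to compare metrics for categorizing cardiotoxicity status". Its stated reason is "considering most patients in the PROACT sub-study of the Survive Registry will have metastatic cancer with prior treatments including chemotherapy". Its consequence is that "physician discretion and patient presentation will provide the final decision on cardiotoxicity category".

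Elsewhere the plan describes the baseline as follows:

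- Section 5.1: "After consenting to the PROACT study, patients will undergo a baseline MRI to determine their risk stratification for the study". The scan is also a gate: "This baseline MyoStrain® MRI must demonstrate 2 or more segments measuring >-10% or 9 or more segments >-17% for entrance into the study".
- Section 2, for all patients who have a cardiac MRI: "a standard non-contrast protocol will be used to acquire a full cardiac volume for chamber sizes and LVEF".
- Section 5.2, on the MyoStrain exam: its measures section "will display resting strain, as well as global circumferential and longitudinal strain".
- Section 11: each patient's longitudinal data are compared with that patient's own baseline, and the cardiotoxicity status comes from a clinical committee. No route through physician discretion is mentioned there.

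On masking, Section 1.3 calls the trial open label. Section 5.1 gives MyoStrain values to physicians in the guided arm and withholds them in the observational arm. Section 11 says that the team receives the full observational-arm data only at the end of the study. No section says whether the committee, or a physician using discretion, knows the arm or the MyoStrain values.

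**The concern.** The trigger does not fit the design. Each randomised patient should have an LVEF and a strain measurement from the entry scan, so at follow-up there is normally a baseline to compare with. Prior treatment explains a missing baseline only if the word means a measurement taken before any cancer therapy, and the plan does not say so.

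This matters because the category is the yardstick for the primary endpoint. A physician who has seen the MyoStrain report and then decides the category by discretion may let the report shape the label. The reference then moves toward the test under study, and the test's sensitivity and accuracy look better than they are. Physicians in the observational arm do not have the report, so the label may also be formed differently in the two arms.

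**Working it through.** The plan gives no figure on this point to reproduce, so the first step is textual.

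**Step 1: two meanings of baseline at follow-up.**

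- *The PROACT entry scan.* Sections 2, 5.1 and 5.2 supply LVEF and GLS for every randomised patient, and Section 11 uses this baseline for individual comparison. The exception is then largely redundant for the imaging criteria.
- *A measurement before any cancer therapy.* Section 1.5 expects most patients to be pre-treated. How many have an earlier scan is not stated, so the share of labels settled by discretion is unknown and could be large.

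**Step 2: who decides.** Section 11 gives the classification to the committee. Section 1.5 begins with the committee but, in the exception, gives the last word to physician discretion. It does not say whether that physician sits on the committee.

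**Step 3: possible size.** None of these inputs is in the documents. Assume true sensitivity Se = 0.70, specificity Sp = 0.80 and prevalence p = 0.30. Let w be the share of all labels that simply follow MyoStrain. Assume the other labels are correct and that following is unrelated to true status.

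- Share testing positive: P(T+) = 0.30 × 0.70 + 0.70 × 0.20 = 0.35.
- Apparent sensitivity = [(1 − w) × p × Se + w × P(T+)] / [(1 − w) × p + w × P(T+)].
- True accuracy = 0.30 × 0.70 + 0.70 × 0.80 = 0.77. A followed label always agrees with the test, so apparent accuracy = (1 − w) × 0.77 + w.

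In every row, half of the discretionary labels that can follow MyoStrain are assumed to do so. The guided-arm rows halve w because allocation is 1:1. The baseline-only rows use one of the seven scheduled exams in Section 5.1 (1/7, about 14% with complete follow-up).

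| Discretion covers | Arms affected | w | Apparent sensitivity | Apparent accuracy |
|---|---|---|---|---|
| Baseline exam only (1/7) | guided | 0.036 | 0.2150 / 0.3018 = 71.2% | 77.8% |
| Baseline exam only (1/7) | both | 0.071 | 0.2200 / 0.3036 = 72.5% | 78.6% |
| 50% of exams | guided | 0.125 | 0.2275 / 0.3063 = 74.3% | 79.9% |
| 75% of exams | guided | 0.1875 | 0.2363 / 0.3094 = 76.4% | 81.3% |
| 50% of exams | both | 0.25 | 0.2450 / 0.3125 = 78.4% | 82.8% |
| 75% of exams | both | 0.375 | 0.2625 / 0.3188 = 82.4% | 85.6% |

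The both-arms rows need a classifier who also sees observational-arm MyoStrain values, for example a committee reading after those data are released at the end of the study. The plan neither states nor excludes this.

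**The case against.** A reader might infer that discretion governs most patients. The text does not say so. The trigger is conditional, and the phrase about most patients describes their metastatic, pre-treated state; it is a reason for the rule, not a count of missing baselines.

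A reader might also infer that the classifier is unmasked. The documents support only that no masking is specified. Observational-arm physicians are not given MyoStrain values, and the committee's access is not described.

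The exception also has proper uses. Section 1.5 has every exam classified, and the baseline exam of a pre-treated patient may have no earlier comparator. Biomarkers form part of both definitions but are not on the PROACT schedule of events. Section 11 lists a category of functional decline without cardiotoxicity for which Section 1.5 gives no criterion. Some judgement would therefore remain even without the exception.

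Finally, anchoring everything to the entry scan could backfire. GLS is a MyoStrain output in this trial (Section 5.2), so applying the GLS criterion to that scan would write the index test into its own reference.

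All of this stands. It narrows the point and shapes the remedy. It does not resolve the undefined baseline, the two decision-makers or the silence on masking.

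**Conclusion.** The point holds in a limited form. The reference for the primary endpoint has a discretionary route whose trigger is hard to reconcile with a mandatory baseline MRI. Section 1.5 and Section 11 disagree on who has the last word, and nothing keeps the classifier from knowing the arm or the MyoStrain result. Following the rule as written can bias the reference toward MyoStrain.

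The size of that bias cannot be derived from the documents. Under the assumed 70% sensitivity, 80% specificity and 30% prevalence, apparent sensitivity runs from about 71% to 82%, that is, 1 to 12 percentage points too high. The upper figures require discretion in 50% to 75% of exams and labels that follow MyoStrain in both arms. The documents establish neither condition, so those figures illustrate the mechanism and should not be quoted as an estimate.

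**What to change.** In Sections 1.5 and 11:

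1. Define baseline as the PROACT baseline MRI for all follow-up exams, and apply the stated LVEF change criteria to it.
2. Keep MyoStrain-derived GLS and segment values out of the reference label used to assess MyoStrain.
3. Make the committee the only decision-maker, working without sight of the arm or the MyoStrain values.
4. Limit discretion to exams with no comparator, such as the baseline exam. Flag each one, and report the primary sensitivity and accuracy with and without them.

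This is a cheap improvement: wording and an adjudication procedure, with no added visits or scans. It has costs. Change is measured from study entry, so damage from earlier therapy does not count as change, and some exams drop out of the sensitivity analysis. With MyoStrain GLS removed, the label also leans more on LVEF, which is one of the comparators. The report should say so when it sets MyoStrain beside LVEF.
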